11.1. Primary Safety Analysis

The primary safety endpoint is 30 day mortality. The data will be analyzed as a binary variable with each subject counted only once. The primary safety analysis is an analysis of all patients according to treatment received. The treatment group difference and 95% confidence interval will be employed to assess the primary safety endpoint.

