4.3 Method of Randomization

Randomization takes place centrally through a commercially available Interactive Web Response System (IWRS). Randomization will occur in a 2:1 ratio to either MIS or MM. The treatment allocation will be balanced by Hemphill Score (0 – 2, 3 – 4) and hemorrhage location (primarily lobar, primarily deep). Once a patient is determined to meet all study eligibility criteria, the Investigator (or authorized team member) obtains the treatment assignment for that subject. Crossover is not permitted after randomization. Once a subject is randomized, the subject is

considered enrolled in the study and that subject must be followed through to the end of study or to subject's termination of consent.

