10.5.3 Per Protocol Sample

In addition to the defined ITT analysis sample, a per-protocol (PP) sample is defined as a subset of the ITT sample. The per-protocol sample will include all randomized subjects that do not have significant protocol deviations (e.g., eligibility violation, crossover).

10.5.4 Safety Analysis (As Treated) Sample:

In the case of cross-overs, a safety sample that is the same as the ITT sample will be examined in which subjects will be analyzed according to the actual treatment received. Subjects who receive Artemis device-based therapy are included in the MIS arm and subjects who receive only medical therapy are included in the MM arm.

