Interim data analysis of the primary efficacy and safety endpoints is planned after 200 subjects have been enrolled. Additional interim analyses will be conducted after every 50 subjects. The interim analyses will include imputing the 180-day mRS score for subjects who do not have 180 day scores. Based on the predictive probability that the study would be a success, the study may be stopped early for futility or enrollment may be stopped based on expected success. The specific mathematical details of the planned analyses are described in the adaptive design report.

If a lack of equipoise for randomization between treatment and control occurs during trial execution, the supplemental adaptive design report provides the details to evaluate the superiority of MIS as compared to the combined MM arms of the MIND trial and any publicly available trial results with randomized MM arms.

5. Decision Rules for Adjusting the Sample Size

The maximum study sample size is 500 subjects and the minimum sample size is 200 subjects. The final study sample size is estimated to be low if the treatment effect is small and the study could be stopped for futility or if the treatment effect is large and the study could be stopped for expected success. The final study sample size will be high if the evidence for the treatment effect is inconclusive. The specific decision rules for sample size adjustments are described in the adaptive design report.

6. Analysis Populations

All primary and secondary effectiveness endpoints will be performed for both the intent-to-treat (ITT) population and per-protocol (PP) population.

- 6.1. Target Population: The target population is patients 18-80 years of age who have a diagnosis of spontaneous, non-traumatic, intracerebral hemorrhage (ICH) ranging in volume between and including 20 and 80 cc, with an associated significant neurological deficit (NIHSS > 6) who do not require emergent open surgical decompression related to uncontrolled intracranial pressure or mass effect.
- 6.2. Intent to Treat Sample: As the primary analysis, all efficacy and safety outcome measures will be analyzed under the intent-to-treat (ITT) principle. Under this principle, the evaluable sample includes all subjects who are randomized. Each subject will be analyzed according to the treatment group to which they were randomly assigned at the time of randomization. This population is the primary population for all efficacy parameters.

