- 6.3. Per Protocol Sample: In addition to the defined ITT analysis sample, a per-protocol (PP) sample is defined as a subset of the ITT sample. The per-protocol sample will include all randomized subjects that do not have significant protocol deviations (e.g. eligibility violation, crossover).
- 6.4. Safety Analysis (As Treated) Sample: In the case of cross-overs, a safety sample that is the same as the ITT sample will be examined in which subjects will be analyzed according to the actual treatment received. Subjects who receive Artemis device-based therapy are included in the MIS arm and subjects who receive only medical therapy are included in the MM arm.

6.5. The following additional population definitions apply to this study:

- 6.5.1.Screened: All patients considered for participation in the study, whether or not they sign an informed consent.
- 6.5.2.Screen Failure: All patients considered for participation in the study, who failed to meet inclusion or met exclusion criteria. Patients can be screen failed based on general or imaging criteria. These patients may or may not have signed an informed consent.
- 6.5.3.Enrolled (Randomized): All subjects who have been randomized based on the result of the baseline imaging and other inclusion/exclusion criteria. Informed consent must be obtained prior to randomization.
- 6.5.4.Completed: All subjects who were enrolled (randomized) and completed the study follow-up or were known to have died prior to the follow-up timepoint. The completed subject metric will be provided for Day 180 and Day 365 follow-up.
- 6.5.5.Early Termination: Subjects who were enrolled (randomized) but did not complete follow-up and were not known to have died. The early termination subject metric will be provided for Day 180 and Day 365 follow-up.

7. Statistical Methods

Summary tables (descriptive statistics and/or frequency tables) will be provided for all baseline variables, efficacy variables, and safety variables, as appropriate. Continuous variables will be summarized with descriptive statistics (n, mean, standard deviation, range, and median).

Frequency counts and percentage of subjects within each category will be provided for categorical data. Based on the variable distribution, parametric or non-parametric tests will be used for comparisons between groups.

8. Baseline Characteristics

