Baseline data will be analyzed to assess the comparability of treatment groups. Baseline data including, but not limited to demographics, clinical characteristics, and baseline ICH characteristics will be summarized using descriptive statistics. Statistical testing will be performed as appropriate.

9. Subject Disposition

The number of subjects for each of the following categories will be summarized.

- Screened patients

- Screen failures
- Randomized (Enrolled) subjects
- Subjects randomized that did not receive assigned treatment
- Subjects completing the study; subjects not completing the study
- Subjects included in the intent to treat population
- Subjects included in the per protocol population
- Subjects included in the safety population

10. Efficacy Analysis

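### The SAP assigns the primary safety endpoint, 30-day mortality, to two different primary analysis sets: treatment received (SAP 11.1) and intent-to-treat (SAP 6.2, protocol 10.5.2)

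*SAP*

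**What the plan says.** **ITT for safety.** SAP 6.2 states: "As the primary analysis, all efficacy and safety outcome measures will be analyzed under the intent-to-treat (ITT) principle". Protocol 10.5.2 carries the same sentence. Both then place each subject in the randomised group.

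**Treatment received for safety.** SAP 11.1, on 30-day mortality, states: "The primary safety analysis is an analysis of all patients according to treatment received". The summary is the group difference with a 95% CI. No hypothesis or margin is given.

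**The as-treated sample.** Protocol 10.5.4 and SAP 6.4 define it conditionally: "In the case of cross-overs, a safety sample that is the same as the ITT sample will be examined". Under its allocation rule, "subjects who receive only medical therapy are included in the MM arm". Protocol 4.3 says: "Crossover is not permitted after randomization".

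**Text that leaves room for an as-treated reading of safety.**
- SAP 6.2 and protocol 10.5.2 both close with "This population is the primary population for all efficacy parameters", which names efficacy only.
- SAP 6 opens with "All primary and secondary effectiveness endpoints will be performed for both the intent-to-treat (ITT) population and per-protocol (PP) population", which does not mention safety.
- SAP 9 lists a separate disposition line, "Subjects included in the safety population".

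**Timing.** Protocol 10.8 and SAP 11.4 set randomisation as day 0 and count deaths through day 30, without naming an analysis set. Protocol 6.7 places the procedure after randomisation.

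**The concern.** This is the trial's only primary safety endpoint, for an invasive procedure, and the documents give it two primary analysis sets. The conflict lies within the SAP (6.2 against 11.1) and between SAP 11.1 and protocol 10.5.2.

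Grouping by treatment received is understandable for device-related adverse events. All-cause death counted from randomisation is different, because a patient must survive to surgery in order to have received it. Under SAP 11.1 read literally, the headline difference and its CI would compare groups formed partly by events after randomisation. An MIS-randomised patient who dies before the procedure has received only medical therapy and could be counted against MM. Unoperated MIS patients who survive would move to MM as well.

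The same endpoint is examined at interims from 200 subjects onward (protocol 10.6, SAP 4), and those sections name no set.

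**Working it through.** **1. Is the conflict resolved anywhere?** SAP 1 describes the SAP as elaborating the protocol's methods but states no order of precedence. SAP 11.3 says the primary safety comparison is specified in the protocol, and the protocol's own rule for safety outcomes is ITT. The efficacy-only sentences listed above do not withdraw safety from the opening sentence of the ITT definition. The text leans toward ITT but does not settle the question.

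**2. Can a pre-surgery MIS death be moved to MM?** The clock starts at randomisation, surgery follows, and SAP 6.4 places medical-only subjects in MM. That sample is triggered by cross-overs, which protocol 4.3 does not allow, and neither document says whether death before surgery is a cross-over. The move is possible under the wording but not certain.

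**3. Size.** The plan gives no planning rate, power or margin for 30-day mortality, so there is no figure of its own to reproduce. The following is illustration only.

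Inputs:
- Arm sizes 333 and 167, from 2:1 allocation of the maximum 500; 133 and 67 at the minimum of 200, which is also the first interim.
- *p*, true 30-day mortality, taken as equal in both arms. The main value is 15%. Protocol 1.3.2.1 reports 9% (surgical) and 15% (medical) at 30 days in the earlier catheter-and-thrombolysis trial, and protocol 1 gives 40% at one month for ICH generally.
- *k*, MIS-randomised patients who die before surgery (assumed).
- *s*, unoperated MIS-randomised patients alive at Day 30 (assumed).

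Formulas, by treatment received:
- MIS rate = (333*p* − *k*) / (333 − *k* − *s*)
- MM rate = (167*p* + *k*) / (167 + *k* + *s*)
- Shift = MIS rate − MM rate. Under ITT the difference is 0.

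Example with *p* = 0.15, *k* = 3, *s* = 0: MIS (49.95 − 3)/330 = 14.23%; MM (25.05 + 3)/170 = 16.50%; shift −2.27 points.

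| Arms | *k* | *s* | Shift (points) |
|---|---|---|---|
| 333/167 | 0.3% of MIS (1.0) | 0 | −0.76 |
| 333/167 | 0.5% of MIS (1.7) | 0 | −1.27 |
| 333/167 | 1% of MIS (3.3) | 0 | −2.52 |
| 333/167 | 3 | 0 | −2.27 |
| 333/167 | 3 | 10 | −0.91 |
| 333/167 | 3 | 17 | 0.00 |
| 333/167 | 3 | 20 | +0.38 |
| 333/167 | 0 | 5 | +0.66 |
| 333/167 | 0 | 10 | +1.31 |
| 133/67 | 1 | 0 | −1.89 |
| 133/67 | 1 | 5 | −0.22 |
| 133/67 | 1 | 6 | +0.11 |

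For the same three percentages with *s* = 0 at 333/167, *p* = 9% gives −0.81, −1.36 and −2.70, and *p* = 40% gives −0.54, −0.89 and −1.78. Rates above 1% are not used, because the earlier trial's whole 7-day surgical-arm mortality was 1%. That is a plausibility check from another trial, not a bound.

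The shift is zero when *k*/(*k* + *s*) = *p*, that is, when *s*/*k* = (1 − *p*)/*p*: 10.1, 5.7 and 1.5 survivors per death at *p* = 9%, 15% and 40%.

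For scale, the ITT 95% CI half-width is 1.96 × √[*p*(1 − *p*)(1/*n*₁ + 1/*n*₀)]. At *p* = 15% this is 6.64 points for 333/167 and 10.48 for 133/67.

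**The case against.** **A specific section may govern a general one.** On that view SAP 11.1 overrides SAP 6.2, whose last sentence names efficacy only. This is arguable, but neither document states such a rule, and SAP 11.3 points back to the protocol, where the rule is ITT.

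**SAP 11.1 may not be the headline.** SAP 11.4 calls Kaplan-Meier the primary method for the mortality rate and names no population, so SAP 6.2 would arguably make that analysis ITT. Disposition counts and the ITT mRS analysis would also expose the deaths. These outputs do limit the harm. However, SAP 11.1 is the section titled as the primary safety analysis, and a second analysis called primary on an unnamed set adds to the ambiguity.

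**A death before surgery is not a cross-over in ordinary usage.** This is fair, and it is why the route is stated only as possible. But SAP 11.1 carries no cross-over condition, so whoever programs the analysis would have to decide.

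**The size is assumed and small.** This stands. Every shift in the table lies inside the CI half-width, the direction is not fixed, and the largest shifts assume no unoperated survivors.

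**The interim set may be named elsewhere.** The adaptive design report and the DSMB charter are not among the documents reviewed and may name it. The interim point holds only for the protocol and SAP text.

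**Conclusion.** The concern holds as an inconsistency that should be fixed. The conflict is plain in the text and does not depend on any calculation.

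Its numerical effect is modest and conditional: about −0.8 points per moved death at 333/167 and −1.9 at 133/67, with 15% mortality in both arms and no unoperated survivors. Enough unoperated survivors would cancel or reverse it. These figures rest on assumed counts of pre-surgery deaths and missed operations, on equal true mortality, and on the literal reading of SAP 11.1 with SAP 6.4. Because SAP 11.1 sets no margin or test, no inflation of error rates is claimed. What is at stake is how the main safety estimate is defined and read.

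**What to change.** - In SAP 11.1, replace analysis by treatment received with analysis by randomised group (ITT). Name the same set in SAP 11.4. This follows the protocol's existing rule.
- Keep the as-treated analysis of SAP 6.4 as supportive.
- List MIS-randomised patients who died before surgery.
- Split the existing SAP 9 line for subjects who did not receive their assigned treatment by arm and Day 30 vital status.

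For consistency, it is also worth stating in SAP 6.4 whether death before surgery counts as a cross-over, and naming the set in protocol 10.8 and the interim sections (SAP 4, protocol 10.6).

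**Cost:** one sentence each in SAP 11.1 and 11.4, one listing and one table split, plus a short sentence at each of the other places if they are aligned. No new patients or data are needed. Dates of death and the disposition count are already planned, and SAP 10.5 already requires the time of sheath placement. The change should be made before unblinding, which is when SAP 1 requires sign-off.

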11.2. Analysis of Adverse Events

Adverse events will be coded using the MedDRA dictionary. The number and percentage of subjects with AEs and SAEs will be summarized by body system and preferred term. Each subject will be counted only once within a category. The specific categories analyzed will be those that are reported by at least three (3) percent of the subjects. The Clinical Events Committee adjudicated data supersedes the investigator reported data in all analyses of adverse events.

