died within 7 days compared to the SOC arm (1% vs 4%, P=0.018, respectively) and also at 30 days (9% vs 15%, P=0.066), respectively. There were 2 bacterial brain infections with 30 days in the MISTIE arm and none in the SOC arm. The MISTIE arm and SOC arm had comparable symptomatic brain bleeds with 72 hours from the last thrombolytic dose (2% vs 1%, P=0.325). However, asymptomatic brain bleeds within 72 hours from the last thrombolytic dose was significantly higher in the MISTIE arm. There were fewer serious adverse events reported in the MISTIE arm compared to the SOC arm (126 events vs 142, P=0.012), which was statistically significant. The authors reported that an exploratory analysis of clot removal did show an association between extent of removal and a lower mRS score (0-3), possibly due to the benefit of the procedure or due to unmeasured confounding effects. Furthermore, the authors concluded that there were few negative consequences to MISTIE, and it was safe with regards to serious bleeding and infection. The procedural risks were also reported as comparable between the two arms.

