- Symptomatic Re-Hemorrhage or New Hemorrhagic Event: Any new intracranial hemorrhage or increase in size of pre-existing hemorrhage (IPH, IVH or extra-axial bleed) within 30 days associated with an NIHSS increase of ≥ 4 or a GCS decrease > 2 persisting for at least 24 hours, requiring emergency surgical decompression or resulting in death.
- Symptomatic Evolution of Perihematomal Edema: Edema with increased mass effect or uncontrolled ICPs within 30 days requiring emergency surgical decompression NOT related to new or increased hemorrhage (i.e. edema related) associated with an NIHSS increase of ≥ 4 or a GCS decrease > 2 persisting for at least 24 hours, requiring emergency surgical decompression or resulting in death.
- Symptomatic Ischemic Stroke: A new ischemic stroke (ipsilateral, contralateral; contiguous with bleed/operative site or remote; cortical, subcortical or perforator distribution) within 30 days associated with an NIHSS increase of ≥ 4 or a GCS decrease > 2 persisting for at least 24 hours, requiring emergency surgical decompression or resulting in death.
- Surgical complications related to MIS: Surgical site infection, brain abscess or confirmed meningitis, or documented complication(s) deemed specifically related to the procedural anesthetic (medication, access or intubation related) within 30 days.

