Statistical Analysis Plan

For CLP 11899

MIND: A Prospective, Multicenter Study of Artemis a Minimally Invasive Neuro Evacuation Device, in the Removal of Intracerebral Hemorrhage

Prepared by: Penumbra Inc.

NCT number: NCT03342664

Date: January 02, 2020

1. Overview

This is a multi-center randomized controlled study designed to compare the safety and efficacy of minimally invasive hematoma evacuation with the Artemis Neuro Evacuation Device to best medical management for the treatment of intracerebral hemorrhage (ICH).

Up to 500 patients will be enrolled from up to 50 global centers (US and OUS). Each site will be limited to a maximum enrollment of up to 120 patients (~20% of total enrollment).

This Statistical Analysis Plan (SAP) will provide details to further elaborate statistical methods as outlined in the protocol and will describe analysis conventions. The SAP will be signed off prior to unblinding.

2. Sample Size

A sample size of up to 500 patients was selected for this study. Based on simulations, this trial has 81% power for a cumulative odds ratio of 1.7 with a one-sided alpha of 0.025. The minimum sample size is 200 patients (approximately 133 MIS and 67 MM).

The Day 180 mRS distribution used for sample size estimation was based on control arm data from the following published studies: MISTIE II (Hanley 2016), STICH (Mendelow 2005), and SICHPA (Teernstra 2003). The distribution of mRS functional outcomes utilized in the sample size estimation is provided in Table 1.

Table 1. Distribution of mRS functional outcomes

mRS Distribution	0	1	2	3	4	5/6
MM	3%	10%	7%	7%	14%	59%
MIS	5%	15%	10%	9%	16%	46%

3. Randomization

Randomization takes place centrally through a commercially available Interactive Web Response System (IWRS). Randomization will occur in a 2:1 ratio to either MIS or MM. The treatment allocation will be balanced by Hemphill Score (0-2, 3-4) and hemorrhage location (primarily lobar, primarily deep).

If a lack of equipoise for randomization between treatment and control occurs during trial execution, the trial randomization assignment will be revised to randomize all patients to the MIS. The minimum sample size for patients assigned to MIS treatment is 133 patients.

4. Interim Analysis

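### SAP 11.2 limits adverse event analysis to categories reported by at least 3% of subjects, with no exemption for SAEs or for the procedural harms that the protocol defines

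*SAP*

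**What the plan says.** SAP 11.2 first promises a summary: "The number and percentage of subjects with AEs and SAEs will be summarized by body system and preferred term". It then sets the frequency rule: "The specific categories analyzed will be those that are reported by at least three (3) percent of the subjects". It does not say whether the 3% is of both arms together or of either arm. Nor does it say whether a category is a body system or a preferred term, or whether the rule limits the tables, the comparisons, or both. No class of event is exempt. The section ends by giving CEC-adjudicated data precedence over investigator reports.

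Protocol 7.6.1 singles out events for detailed forms and narratives: death, symptomatic re-hemorrhage, symptomatic perihematomal edema, symptomatic ischemic stroke, and a procedural group that begins "Surgical complications related to MIS: Surgical site infection, brain abscess or confirmed meningitis". Protocol 12.2 has the same events assessed by the medical monitor and presented to the DSMB. Of these, only death has its own by-arm analysis in the SAP (11.1 and 11.4).

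Protocol 10.1 gives as one aim of the treatment arm a prospective, independently adjudicated account of the technical results and complication rates of the Artemis procedure.

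**The concern.** A frequency cut keeps common background events from crowding the safety analysis. Applied without exemptions, it also removes the events for which a device trial most needs a comparison: uncommon, serious, and tied to the procedure. The protocol's own background shows the scale. Of the phase III trial of catheter evacuation with thrombolysis it reports: "There were 2 bacterial brain infections with 30 days in the MISTIE arm and none in the SOC arm". With 250 patients in the surgical arm that is 2/250 = 0.8%.

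If the rule is followed as written, such an event would have no planned between-arm analysis in the final report, whatever the imbalance. Narratives and DSMB review protect subjects during the trial, but they do not supply the complication rates with intervals that Protocol 10.1 leads the reader to expect. Preferred-term tables do not fill the gap either, because the Protocol 7.6.1 events are composites with their own criteria (for re-hemorrhage, for example, an NIHSS or GCS change, a decompression or death, within 30 days).

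**Working it through.** **Inputs.** The cut is 3% (SAP 11.2). On allocation, the SAP says: "Randomization will occur in a 2:1 ratio to either MIS or MM". On size: "The maximum study sample size is 500 subjects and the minimum sample size is 200 subjects". The documents give no expected complication rates for Artemis, so the true MIS rates below (1% to 5%, with none in MM) are assumptions shown as a range.

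**The plan's own figures.** The 3% is a chosen rule with no derivation, so there is nothing to reproduce. The SAP's split at the minimum size does reproduce: 200 × 2/3 = 133.3 and 200 × 1/3 = 66.7, stated as 133 and 67. At N = 500 the same ratio gives 333 and 167.

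**Count needed**
- Pooled reading: 0.03 × 500 = 15 subjects; 0.03 × 200 = 6.
- Per-arm reading, MIS arm: 0.03 × 333 = 9.99, so 10 subjects; 0.03 × 133 = 3.99, so 4.

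**Rate needed for an MIS-only event on the pooled reading.** 15/333 = 4.5% at N = 500, and 6/133 = 4.5% at N = 200.

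**Chance that an MIS-only event falls short of the cut.** This is P(X ≤ count − 1), with X binomial on the MIS arm size and the assumed true rate.

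| True MIS rate | N = 500, pooled (≤ 14 of 333) | N = 500, per arm (≤ 9 of 333) | N = 200, pooled (≤ 5 of 133) | N = 200, per arm (≤ 3 of 133) |
|---|---|---|---|---|
| 1% | > 99.9% | 99.8% | 99.8% | 95% |
| 2% | 99.7% | 87% | 95% | 72% |
| 3% | 92% | 46% | 79% | 43% |
| 4% | 64% | 14% | 56% | 22% |
| 5% | 30% | 3% | 34% | 10% |

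**What an excluded imbalance can look like.** On the pooled reading at N = 500, 14 of 333 (4.2%) against 0 of 167 is one subject short of the cut. Fisher's exact two-sided p is 0.007.

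**Role of the 2:1 ratio (pooled reading, N = 500).** An MIS-only event needs 15/333 = 4.5% of its arm. Under 1:1 it would need 15/250 = 6.0%. An MM-only event under 2:1 needs 15/167 = 9.0%.

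**A commoner event.** Protocol section 3 reports re-bleeding in 2 of 29 subjects (6.9%) with the predecessor device. At that rate in MIS alone, the expected count is 333 × 0.069 = 23.0 against 15 needed, and the event clears the pooled cut with probability 97%. At N = 200 it is 133 × 0.069 = 9.2 against 6, with probability 90%.

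**An event in both arms.** The phase III trial had symptomatic bleeds of 2% and 1%. Those rates here would give 333 × 0.02 + 167 × 0.01 = 8.3 subjects of 500 (1.7%), below the pooled count of 15.

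**The case against.** The strongest reply is that the SAP does not say rare events go unreported. The sentence before the rule promises AE and SAE summaries by preferred term with no cut, and SAP 7 promises summary tables for safety variables as appropriate. On that reading everything is tabulated and the 3% limits only further analysis. This stands. A reader might infer that rare harms would vanish from the report, and the text does not support that. What remains is that they have no planned comparison, and that the SAP leaves open how the two sentences fit together.

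Second, the pooled denominator is an inference, since the SAP says only that the percentage is of the subjects. This also stands, so the pooled figures are conditional. The per-arm columns show that the problem shrinks but remains for events at 2% or below.

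Third, a reader might blame the 2:1 allocation for diluting MIS harms. The arithmetic runs the other way: on the pooled reading 2:1 lowers the MIS-only hurdle from 6.0% to 4.5%, and MM-only events face the higher one.

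Fourth, a reader might infer that bleeding as a whole would drop out. At the predecessor device's 6.9% it would usually be kept, though that figure comes from 29 subjects and is not limited to symptomatic events. The 2% and 1% rates come from a procedure with thrombolysis and a 72-hour window, so they carry over only loosely.

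Fifth, not every listed harm is MIS-only. Protocol section 3 expects re-bleeding, abscess and meningitis whatever the arm. If categories are body systems, a rare event could also pass within a commoner group. Both are fair limits on the table, although passing inside a broad body system would not give the event its own comparison.

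Finally, oversight is not weak. Medical-monitor review, CEC adjudication, narratives and DSMB presentation carry no frequency cut, and death is analyzed separately. That answers a concern about safety monitoring, but not one about the final analysis.

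**Conclusion.** The point holds as a gap in the final safety analysis. SAP 11.2 sets a 3% rule with no exemption for SAEs, device- or procedure-related events or the Protocol 7.6.1 events, and apart from death no other SAP section gives those events a by-arm analysis. That conflicts with the aim stated in Protocol 10.1.

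The size depends on two assumptions: the denominator, and an event confined to MIS at a rate the documents do not supply. Under either denominator, an MIS-only harm at 2% or below is more likely than not to be left out, at both N = 200 and N = 500. At 3% to 4% the answer depends heavily on the denominator, and commoner harms would mostly be kept. The primary efficacy and mortality analyses are unaffected. This is an inexpensive improvement that should be made before the safety data are analyzed.

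**What to change.** In SAP 11.2:

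1. Apply the 3% cut to non-serious AEs only, and count a category as meeting it if either arm reaches 3%. Say whether a category is a body system or a preferred term, and whether the cut governs tables or only comparisons.
2. Report by arm, with no threshold and with exact 95% CIs: all SAEs, all device- or procedure-related events, and each event as defined in Protocol 7.6.1. Use the CEC-adjudicated data, which the SAP already ranks first.

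The second step is essential. Changing the denominator alone would still leave out a 2% MIS-only event 87% of the time at N = 500.

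No new data are needed, since the protocol already collects these events. The cost is SAP wording, longer safety tables, and more unadjusted comparisons. SAP 11.3 already treats such comparisons as secondary and outside labeling claims, so the added intervals should be read as descriptive.
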